8.8 STATISTICAL ANALYSIS

A descriptive analysis of all dependent variables, as well as demographic variables, will be performed, expressing them as mean \pm standard deviation or, where appropriate, as median and range (min-max), according to the normality of the data; nominal variables will be expressed as frequencies. Subsequently, an intragroup inferential analysis will be carried out for weight, waist circumference, abdominal circumference and blood pressure with ANOVA for repeated samples with Tukey *post hoc*, and in case the data distribution does not meet the normality criteria, the corresponding nonparametric test will be performed (e.g.,

Friedman, followed by Dunn's *post hoc*). For biochemical analysis (glycemic and lipid profile and markers of inflammation), as well as the evaluations corresponding to diabetic peripheral and autonomic neuropathy, and quality of life, a Student's T test will be performed for dependent groups, or where appropriate, with Wilcoxon.

The intergroup comparison will be made with Student's T test for independent samples, or if applicable, with Mann-Whitney U at each measurement time. A $p < 0.05$ will be considered as statistical significance. All of the above will be carried out using version 5 of the GraphPad Prism software.

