8. METHODOLOGY

8.1 Study Type: Explanatory

8.2 Design: Double-blind, randomized controlled clinical trial.

8.3 Study population: Adult subjects aged 40-60 years diagnosed with type 2 diabetes mellitus and diabetic neuropathy who attend, by open call, to Anáhuac México Norte University, the Kidney Specialty Center in the State of Mexico, and the Nueva Oxtotitlán clinic (Toluca).

8.4 Sample Size Calculation:

$$N = \frac{2(Z\alpha+Z\beta^2)s^2}{d^2} = N = \frac{2(1.96+0.84^2)(0.84)^2}{(0.776)^2} = N = \frac{(15.68)(0.7056)}{(0.6021)}$$

A total of 18 subjects per group were obtained, considering the following data:

s= Baseline standard deviation: 0.84 (obtained from a study in which probucol and methylcobalamin are used in subjects with DN and the TCSS is used to assess the effect of the intervention.) (49)

d= Proposed difference: 0.776 (refers to the expected difference → 7.5% decrease with respect to the control group)

Z α = 1.96 (value in tables, corresponding to a significance level of 95% for two tails)

Z β = 0.84 (value in tables, corresponding to a power of 80%)

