Patients will be asked to attend the appointments on an empty stomach, after having urinated and defecated. Weight will be determined according to the Lohman technique, that is, without shoes and with as few clothes as possible, the individual will be placed in the center of the scale and must remain still during the measurement. (54) Waist circumference will be measured according to the proposal of the Ministry of Health of Mexico: placing the tape in a horizontal plane around the waist, taking as reference the mid-axillary line, locating the midpoint between the lower costal margin and the highest lateral edge of the iliac crest (55) and the abdominal circumference: the upper part of the hip bone and the upper part of the right iliac crest are located and the measuring tape is placed in a horizontal plane around the abdomen, at the level of the iliac crest, at the end of a normal expiration. (55) Likewise, blood pressure will be measured using a sphygmomanometer (Nebucor brand, model HL-888JA), according to the Clinical Practice Guide for the Diagnosis and Treatment of Arterial Hypertension in the first level of care (57). These evaluations will be carried out every month, until completing the three months of the duration of the study. In addition, at the beginning of the study the MNSI (Annex 3) will be applied as part of the diagnosis of DN, and both at the beginning and at the end, the TCSS (Annex 4), the questionnaire as the physical examination (51), the BEST questionnaire (Annex 5), the Bristol scale (Annex 6) and the Diabetes 39 quality of life questionnaire (Annex 7) will be applied and laboratory studies will be taken to know the biochemical parameters (triglyceridemia, HDL-c, LDL-c, glycemia,

HbA1c, TG / HDL index and neutrophil/lymphocyte ratio will be determined, as described in the table of variables.

Participants in both groups, being subjects with a cardiometabolic disease, will be nutritionally assisted, that is, all patients will be given a meal plan according to the characteristics of each one of them, calculated by the Mifflin-St. Jeor energy expenditure prediction formula (67) for subjects with obesity, while, according to the Joslin Diabetes Center, a distribution of 40-45% carbohydrates, 30-40% lipids, and 20-30% protein is suggested. (68) Two capsules will be prescribed – cocoa for the experimental group or methylcellulose for the control group – in the morning and two capsules at night.

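### The within-arm ANOVA with Tukey on the four monthly measures has no safeguard if patients change at different rates, and the month-3 arm comparison of these measures ignores baseline (minor)

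*Combined protocol and SAP*

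**What the plan says.** Section 8.7 sets four visits: baseline and months 1, 2 and 3. Of weight, waist circumference, abdominal circumference and blood pressure it says: "These evaluations will be carried out every month, until completing the three months of the duration of the study". It also says that "all patients will be given a meal plan according to the characteristics of each one of them", so both arms start a diet at baseline.

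Section 8.8 plans two kinds of test for these measures.

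- **Within each arm:** "an intragroup inferential analysis will be carried out for weight, waist circumference, abdominal circumference and blood pressure with ANOVA for repeated samples with Tukey" as the post hoc procedure. Friedman with Dunn replaces it if normality fails.
- **Between arms:** Student's t test or, where applicable, a comparison "with Mann-Whitney U at each measurement time".

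The threshold is the same throughout: "A $p < 0.05$ will be considered as statistical significance". The plan does not mention sphericity, an epsilon correction, errors specific to each contrast, or adjustment for baseline. The neuropathy, laboratory and quality-of-life outcomes are tested within arm by a paired t test or Wilcoxon.

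**The concern.** Standard repeated-measures ANOVA takes one error mean square from all visits, and Tukey applies it to all six pairs of visits. That is correct only under sphericity, meaning that the difference between any two visits has the same variance. A normality check does not test this, because data can be perfectly normal and still violate it.

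Here a violation is plausible. If individual meal plans lead patients to lose weight or waist at different rates, their values spread apart over time. The month-3 minus baseline difference is then more variable than the difference between neighbouring visits. The pooled error lies between the two, so baseline versus month 3, the contrast a reader will look at first, is tested too liberally. Adjacent visits are tested too conservatively.

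Between arms, each visit is tested on its raw values. The baseline value of the same measure is available for every analysed patient and is not used.

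**Working it through.** **Inputs from the documents**

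- Four visits at months 0, 1, 2 and 3 (section 8.7).
- Significance at 0.05 (section 8.8).
- 18 patients per group (section 8.4).

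The 18 comes from the TCSS calculation, with z values "corresponding to a significance level of 95% for two tails" and "corresponding to a power of 80" percent, "s= Baseline standard deviation: 0.84" and a difference of 0.776. It reproduces: 2 × (1.96 + 0.84)² × 0.84² / 0.776² = 15.68 × 0.7056 / 0.6022 = 18.4, stated as 18. It is used here only as the number of patients per arm.

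**Assumption, not in the documents.** Each patient has a personal slope with SD τ per month and independent visit noise with SD σ. Let k = τ/σ, varied from 0 to 2. The true mean change is zero.

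**Standard errors.** In units of σ², two visits g months apart differ with variance 2 + g²k².

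- Baseline to month 3 (g = 3): 2 + 9k².
- Adjacent visits (g = 1): 2 + k².
- Pooled over six pairs (three with g = 1, two with g = 2, one with g = 3): mean g² = (3×1 + 2×4 + 1×9)/6 = 20/6 = 3.33, so 2 + 3.33k².

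The baseline-to-month-3 SE is understated by a factor of √[(2 + 9k²)/(2 + 3.33k²)]. At k = 1 this is √(11/5.33) = 1.44, and it cannot exceed √(9/3.33) = 1.64. The adjacent-visit SE is overstated by √[(2 + 3.33k²)/(2 + k²)], which at k = 1 is √(5.33/3) = 1.33.

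**Error rates.** These were simulated for one arm of 18, with 20,000 trials per setting, a Tukey critical value of 3.756 and (18 − 1)(4 − 1) = 51 degrees of freedom.

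| k | SE baseline–month 3 understated | SE adjacent visits overstated | Tukey error, baseline–month 3 alone | Tukey family-wise error |
|---|---|---|---|---|
| 0 | 1.00× | 1.00× | 1.0% | 5.0% |
| 0.25 | 1.08× | 1.03× | 1.8% | 5.4% |
| 0.5 | 1.22× | 1.12× | 3.6% | 5.9% |
| 1 | 1.44× | 1.33× | 7.4% | 8.0% |
| 2 | 1.57× | 1.60× | 10.6% | 10.6% |

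With 60,000 trials per setting the family-wise figures are 5.0%, 5.1%, 5.7%, 8.1% and 10.7%, so the rise at k = 0.25 is within simulation noise.

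**After the change.** With paired differences, each tested on its own error with Holm adjustment over six pairs, family-wise error stays between 2.8% and 4.6% over the same range. With no true change, Holm makes a false rejection exactly when Bonferroni does, because the first step is the same.

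**Between arms.** Section 8.5 removes patients who miss an intermediate or the final consultation, so the analysed data are complete. On complete data, a mixed model with arm, visit, arm-by-visit and unstructured covariance returns the same month-3 arm difference and SE as the planned t test. Only a baseline term changes the precision. With baseline-to-month-3 correlation ρ (assumed), the variance falls to about 1 − ρ²:

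- ρ = 0.3: 1 − 0.09 = 0.91
- ρ = 0.6: 1 − 0.36 = 0.64
- ρ = 0.9: 1 − 0.81 = 0.19

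**The case against.** The strongest reply is about size and scope, and most of it stands.

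- **Size.** The ratio k is unknown. At 0.25 or below, family-wise error is essentially nominal. At 0.5 the baseline-to-month-3 comparison alone still errs less than 5% of the time. A noisy measure such as blood pressure may well have a low ratio.
- **The null.** The simulation assumes no mean change within an arm, yet both arms receive a diet. If the diet works, a within-arm rejection is not a false positive. In any case, within-arm change cannot isolate the effect of cocoa. This limits what the error rates mean in practice, but it does not make the pooled SE right.
- **Scope.** The TCSS, laboratory and quality-of-life outcomes use tests of two time points, where sphericity does not arise. The between-arm tests are also free of it.

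Two stronger readings are tempting, and the documents support neither. A reader might infer that a longitudinal model would by itself sharpen the arm comparison. Without a baseline term it reproduces the planned month-3 t test. A reader might also infer that averaging months 1 to 3 recovers wasted precision. At an assumed visit correlation of 0.6 and a constant effect, the average has (1 + 2 × 0.6)/3 = 0.73 of the single-visit variance. If the effect instead builds linearly, the average carries only (1/3 + 2/3 + 1)/3 = 2/3 of the month-3 effect, and relative efficiency is (2/3)²/0.733 = 0.61. That is a choice of estimand, and the documents give neither the correlation nor the time course.

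**Conclusion.** The point holds, at minor severity. For four supporting outcomes, the parametric within-arm analysis relies on equal variances of difference that the plan neither checks nor corrects for, in a setting where patients may well diverge over time. The harm ranges from none to a doubling of the nominal 5%. It is negligible up to a slope-to-noise ratio of about 0.25 and material from about 0.5 to 1 upward. The figures rest on 18 patients per arm, linear patient slopes, independent visit noise and the standard pooled error. The plan does not state its error term, and it names no alternative.

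Separately, the month-3 arm comparison of these outcomes leaves out baseline. The gain from including it depends on a correlation that the documents do not give.

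This does not support any doubt about the TCSS result or the validity of the between-arm tests.

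**What to change.** In section 8.8, for weight, waist circumference, abdominal circumference and blood pressure:

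1. Replace the Tukey comparisons with paired differences, each using its own standard error, with Holm adjustment across the visit pairs reported.
2. If an omnibus repeated-measures F test is kept, apply the Greenhouse-Geisser correction.
3. Replace the month-3 t test between arms with a baseline-adjusted comparison. This can be ANCOVA, or a mixed model with baseline, arm, visit, arm-by-visit and unstructured covariance. Report the month-3 arm difference with its 95% CI.

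No new data are needed. The cost is SAP wording, possibly different software, and slightly less power for within-arm comparisons, adjacent visits included, when sphericity does hold, since each paired contrast has 18 − 1 = 17 degrees of freedom instead of 51.

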
independent samples, or if applicable, with U Mann Whitney, considering $p < 0.05$ as statistical significance and using GraphPad Prism software version 5.

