6. HYPOTHESIS

Cocoa supplementation has a beneficial impact on the biochemical and clinical profile and somatosensory processing of diabetic peripheral and autonomic neuropathy.

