8.6 Study Variables

Type	Variable	Conceptual Definition	Operational Definition	Indicator (unity)	Scale
Independent	Cocoa supplementation	Cocoa powder capsules	4 cocoa powder capsules providing 50 mg of flavonoids (12.5 mg per capsule), administering two capsules in the morning and two capsules at night, every day, for three months. (Appendix 2)	Present (supplement) / Absent (placebo)	Qualitative nominal dichotomous
Dependent	Peripheral diabetic neuropathy	Presence of signs and/or symptoms of peripheral nerve dysfunction in people with diabetes, after excluding other causes. (50)	
It is obtained after applying the MNSI questionnaire regarding symptoms (filled out by the patient and with a maximum score of 13 points) and the physical examination (evaluated by the researcher) with a maximum score of 13 points. (Appendix 3) (51)
 
Toronto Clinical Scoring System: is a clinical evaluation system carried out by the researcher, assigning a score to the symptoms, reflexes and sensory tests. (33, 34) (Appendix 4)
 
H reflex test: This is performed by electrical stimulation, placing the active electrode on the Achilles tendon, the positive electrode above the gastrocnemius and the reference electrode at the height of the gastrocnemius heads. Stimulation is carried out behind the knee (anatomical site of the tibial nerve). The electrical stimulus consists of the application of 10 pulses (1 every 10 seconds) and the maximum intensity applied is according to the sensitivity and tolerance of each individual. (18, 36)
	
Total sum of points obtained from the application of the MNSI questionnaire No unit
 
6-8 points: mild DN 9-11 points: moderate DN 12-19 points: severe DN
 
Total sum of points obtained from the application of the TCSS No unit
 
Quotient R2/R1 μV
	Discrete quantitative Qualitative ordinal Discrete quantitative Discrete quantitative

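### Section 8.8 tests about 17 outcomes at p<0.05 with no primary outcome and no adjustment across outcomes, and does not say that conclusions about cocoa rest on the between-arm tests

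*Combined protocol and SAP*

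**What the plan says.** **Between-arm tests.** Section 8.8: "The intergroup comparison will be made with Student's T test for independent samples, or if applicable, with Mann-Whitney U at each measurement time". The sentence names no outcome. One threshold, p<0.05, "will be considered as statistical significance". The summary repeats the plan and attaches p<0.05 "as statistical significance and using GraphPad Prism software version 5" to its between-arm sentence.

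**Within-arm tests.** These come first in section 8.8: "Subsequently, an intragroup inferential analysis will be carried out for weight, waist circumference, abdominal circumference and blood pressure with ANOVA for repeated samples", with Tukey or Dunn follow-up. Paired t or Wilcoxon tests are planned for the biochemical, neuropathy and quality-of-life measures.

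**Outcomes.** Section 7.1 lists objectives in three domains without ranking them, and no outcome is called primary anywhere. The variables table (8.6) gives the H-reflex outcome once, as "Quotient R2/R1". Section 8.7.1 measures the ratio at four frequencies and reads dysfunction from any of them.

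**Sample size.** Section 8.4 takes its SD from a study in which "the TCSS is used to assess the effect of the intervention". It defines the target difference as a "7.5% decrease with respect to the control group".

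**Diet.** Under section 8.7 both arms receive an individual meal plan. Section 9 says the nutrition plan is partly meant to support metabolic control.

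**The concern.** There are two gaps.

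First, with many outcomes, one threshold and no primary, the plan does not say which result would count as evidence that cocoa works. Tukey and Dunn handle visits within one variable in one arm; they do nothing across outcomes. A reader of the results could not tell a planned success from the best of many chances.

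Second, the within-arm tests are inferential, and the plan does not say that they cannot by themselves support a conclusion about cocoa. Because both arms are put on a diet, HbA1c, glucose, lipids or weight may improve in the cocoa arm with no cocoa effect at all. A significant before/after change there, beside a non-significant one under placebo, is not a comparison of the arms.

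At stake is the false-claim rate of a trial whose sample size was calculated for one two-sided comparison at 0.05.

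**Working it through.** **1. The plan's own figure.** Inputs from section 8.4: SD 0.84, difference 0.776, Z values 1.96 (two-sided) and 0.84.

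- 2 × (1.96 + 0.84)² = 2 × 7.84 = 15.68, the value the protocol uses. The typeset formula squares only the second Z, but 15.68 shows that the sum was squared.
- n = 15.68 × 0.7056 / 0.6021 = 18.4 per group. The protocol states 18; rounding up gives 19.

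So 18 is sized for a single comparison at two-sided 0.05.

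**2. Counting outcomes** (sections 7.1, 8.6 and 8.7):

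- HbA1c and glucose: 2
- triglycerides, HDL-c, LDL-c, TG/HDL: 4
- neutrophil/lymphocyte ratio: 1
- weight, waist, abdominal circumference, waist-to-height ratio: 4
- blood pressure: 1
- TCSS, BEST, Bristol, Diabetes 39: 4
- H2/H1: 1

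The sum is 17. Waist-to-height ratio is absent from the within-arm list in 8.8; without it the count is 16. The count rises to 18 if systolic and diastolic pressure are separated, and further if the four H2/H1 frequencies or the five Diabetes 39 sections are tested separately. MNSI is left out because section 8.7 applies it at baseline for diagnosis. Bristol has no single favourable direction (hard stools at 1, watery at 7), so 16 of the 17 outcomes can favour cocoa.

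**3. Error rates with no cocoa effect, one month-3 test per outcome.** If the tests were independent:

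- any significant difference: 1 − 0.95^17 = 0.582
- any result favouring cocoa: 1 − 0.975^16 = 0.333

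Independence is not plausible: TG/HDL and waist-to-height ratio are computed from other listed outcomes. The documents give no correlations, so a common value is assumed. Simulation of 40,000 trials, 18 per arm, two-sample t tests:

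| Assumed correlation | Any favouring cocoa (16) | Any difference (17) |
|---|---|---|
| 0 | 33.1% | 58.3% |
| 0.3 | 24.8% | 49.6% |
| 0.5 | 19.2% | 39.6% |
| 0.7 | 13.5% | 27.5% |
| *nominal, one test* | *2.5%* | *5%* |

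Repeat runs of 20,000 trials agreed to within about one percentage point. Dropping waist-to-height ratio moves the favouring-cocoa figure from 25% to 24% at correlation 0.3.

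**4. Repeated visits.** Five measures are taken monthly (weight, two circumferences, waist-to-height ratio, blood pressure), so testing at each time gives 5 × 3 + 12 = 27 post-baseline between-arm tests. At an assumed correlation over time of 0.8 to 0.95, the favouring-cocoa figure becomes about 16% (outcome correlation 0.7) to 31% (0.3). The table above is therefore the milder case.

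**5. Power of a single TCSS test at 0.05** (noncentral t):

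- 18 per arm, SD 0.84: effect 0.776 / 0.84 = 0.924; noncentrality 0.924 × √(18/2) = 2.77; 34 degrees of freedom; power 76.8%.
- An assumed 14 per arm, SD 0.84: about 65%.
- 18 per arm, an assumed SD of 1.5: about 33%.
- 18 per arm, SD 0.84, Bonferroni over 17 outcomes (0.05/17 = 0.0029): about 35%.

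**The case against.** The strongest reply is that the plan already implies the answer. Section 8.4 sizes the trial on TCSS relative to control, the summary puts p<0.05 in its between-arm sentence, and the design is a randomised controlled trial. A sympathetic reader would take TCSS and the between-arm comparison as central. That is fair as inference, but sizing on TCSS ties no conclusion to it, and 8.8 never refers back to it. Nor can the study be excused as exploratory: section 8.1 calls it explanatory, section 6 states a directional hypothesis, and no outcome is labelled exploratory.

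Three limits stand. Seventeen is a reading of the objectives and variables table, not a list in 8.8 and not a floor. The correlations are assumptions. And 8.8 nowhere says that within-arm results will be used to claim a cocoa effect; the fault is that it does not exclude this.

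A reader might also infer from the hypothesis, "Cocoa supplementation has a beneficial impact on the biochemical and clinical profile and somatosensory processing of diabetic peripheral and autonomic neuropathy", that success needs significance in all three profiles, which would make the plan very strict. The documents do not support that. It is a broad research hypothesis, and no section turns its wording into a decision rule.

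**Conclusion.** The concern holds. Section 8.8 leaves open which result would support the hypothesis, applies one p<0.05 threshold to about 17 outcomes (16 without waist-to-height ratio), and adjusts nothing across them. With no cocoa effect, 18 per arm and month-3 tests only, at least one significant result favours cocoa in about 13-25% of trials, and some significant difference appears in about 28-50%, for assumed correlations of 0.7 to 0.3.

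These rates apply if any one outcome may count. The plan does not say that it may, so they are not the error rate of a stated rule. But a success rule chosen after seeing the data can always settle on whichever outcome worked, which puts the error at or near these figures, not somewhere between them and 2.5%.

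The 58% obtained under independence should not be quoted as the plan's error rate, because some outcomes are functions of others. The within-arm gap is separate and has not been quantified: its size depends on how much the shared diet changes each outcome, which the documents do not give.

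**What to change.** In section 8.8:

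- (a) Name the between-arm difference in total TCSS at month 3 as the single primary test, two-sided 0.05, consistent with 8.4. Section 10 scheduled statistical analysis for January-June 2022 and the document was last updated in March 2025. If data have already been analysed, label the choice post hoc; naming it now would not restore prespecification.
- (b) State that conclusions about cocoa rest on between-arm contrasts. Report within-arm changes descriptively, with confidence intervals.
- (c) Label all other outcomes and the month 1-2 comparisons exploratory, with estimates and intervals. Say whether blood pressure is one outcome or two, H2/H1 one or four, and Diabetes 39 a total or five sections.

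The cost is wording, with no new data. Some secondary and within-arm p-values would no longer count as significant. TCSS keeps its full alpha, whereas Bonferroni over all 17 would roughly halve its power. The 77% should be quoted with its conditions: section 8.5 eliminates patients for low adherence, missed visits and drug changes, section 8.4 adds no allowance for this, and the SD is a baseline value from a study of another treatment.

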8.5 Selection criteria

Inclusion Criteria	Non-inclusion Criteria

 - Adults aged 40-60 years with a diagnosis of type 2 diabetes mellitus (T2D) and diabetic neuropathy - Minimum duration of T2DM diagnosis: 5 years. - MNSI (Michigan Neuropathy Screening Instrument) score ≥ 2. - Both genders. - Must sign the informed consent form 	
 - Subjects with known sensitivity or hyperreactivity to cocoa or any of its components. - Pregnant women. - Subjects with neurological diseases, such as multiple sclerosis, epilepsy, or previous cerebrovascular events. - Subjects with implanted electronic devices, e.g., pacemakers. - Subjects with peripheral nerve damage in the lower extremities caused by trauma.

	
 - Subjects with a diagnosis of disc herniation below T10. - History/diagnosis of herpes zoster. - Serological diagnosis of rheumatoid arthritis or systemic lupus erythematosus. HIV/AIDS. - Venous insufficiency (C2-C6 class, asymptomatic/symptomatic according to Nicolaides CEAP classification) in lower limbs. - Clinical hypothyroidism. - Use of orthopedic equipment (e.g., prosthetics, splints, wheelchair, crutches). - Cancer diagnosis, use of oncological drugs and/or radiotherapy, or history of cancer or tumors treated with oncological drugs or radiotherapy. - Smoking, considered positive in those with a smoking index greater than 10. - History of diabetic foot (Wagner Scale 3-5) or amputation. - Presence of ulcers and open and/or extensive wounds (>2 cm) - Allodynia - Sciatic nerve root compression - Gout/Hyperuricemia
--	---

Elimination Criteria

- Subjects who modify their pharmacological treatment during the study.
- Subjects who do not attend one of the intermediate consultations
- Subjects who withdraw informed consent or decide not to continue participating in the

study

- Subjects with less than 80% adherence to cocoa supplementation
- Subjects who miss more than one consultation or do not attend the final consultation.

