8.7 STRATEGIC PLAN

Through an open invitation, subjects living with T2D who meet the inclusion criteria will be invited to be assessed and tested at Anáhuac México Norte University, the Kidney Specialty Center, and the Nueva Oxtotitlán Clinic (Toluca), as appropriate. The invitation will be extended, explaining the procedures, duration, and ethical issues; if the subject decides to participate, he or she will be asked to sign the informed consent letter (Annex 1). Once the subject enters the protocol, he or she will be randomized (using a random number table previously generated in a spreadsheet) to the experimental group (diet + capsules with cocoa) or the control group (diet + capsules with methylcellulose).

The study will last three months and patients will be seen on four occasions: at the beginning (baseline measurement), at the first and second month (review appointments) and at the third month (final measurement).

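### Naming Welch's t-test for the between-arm comparisons would be a cheap safeguard: final arm sizes may differ, and the pooled Student's t-test is accurate only if sizes or spreads match.

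*Combined protocol and SAP*

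**What the plan says.** Section 8.8 sets the between-arm analysis for every outcome: "The intergroup comparison will be made with Student's T test for independent samples, or if applicable, with Mann-Whitney U at each measurement time". The significance rule is "A $p < 0.05$ will be considered as statistical significance". The Summary names the same pair of tests. Non-normality is the only condition section 8.8 gives for moving to a nonparametric test. It mentions no check of variances and no unequal-variance version of the t-test. It specifies p-values and descriptive summaries, but no confidence intervals.

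Section 8.4 plans 18 per group with one SD for both arms ("s= Baseline standard deviation: 0.84") and a target of "d= Proposed difference: 0.776" on the Toronto Clinical Scoring System (TCSS).

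Two other places bear on final arm sizes:
- Section 8.7 describes the allocation as "using a random number table previously generated in a spreadsheet" and mentions neither blocks nor a constraint on the ratio.
- The elimination criteria in section 8.5 remove randomised patients for changed medication, missed visits, withdrawal, and low adherence ("Subjects with less than 80% adherence to cocoa supplementation").

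**The concern.** The pooled t-test estimates one common variance. With equal arms its standard error is right even if the spreads differ, and with equal spreads it is right even if the sizes differ. When both differ, it gives too much weight to the larger arm's variance. The standard error is then too small if the smaller arm is the more variable one, and too large in the reverse case.

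The plan aims for equal arms but describes nothing that would keep them equal. Mann-Whitney does not fill the gap, because no variance condition leads to it. The between-arm contrast is the trial's only randomised comparison, so its p-value should mean what it says. Naming a different t-test is enough to remove the dependence on equal spread.

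**Working it through.** **Inputs from section 8.4.** Two-sided 5% (Z = 1.96), 80% power (Z = 0.84), SD 0.84, difference 0.776, 18 per group.

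**The plan's own figure.** n = 2(Zα + Zβ)²s²/d² = 2 × 2.80² × 0.7056 / 0.6021 = 15.68 × 0.7056 / 0.6021 = 18.37. The stated 18 is reproduced; rounding up would give 19. The printed formula squares only Zβ, but the plan's own 15.68 shows that the sum was squared. Exact pooled-t power at 18:18 is 76.8%.

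**How far the pooled standard error is off.** The expected pooled variance is [(n₁−1)s₁² + (n₂−1)s₂²]/(n₁+n₂−2). Its standard error uses that variance times (1/n₁ + 1/n₂). The true squared standard error is s₁²/n₁ + s₂²/n₂.

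- 22 patients with SD 1, 14 with SD 1.5: pooled variance (21 + 29.25)/34 = 1.478; squared SE 1.478 × 0.1169 = 0.1728; true value 0.0455 + 0.1607 = 0.2062; SE ratio √(0.1728/0.2062) = 0.92.
- 22 with SD 1.5, 14 with SD 1: pooled variance (47.25 + 13)/34 = 1.772; squared SE 0.2071; true value 0.1737; SE ratio 1.09.
- 18:18: both expressions equal (s₁² + s₂²)/18, so the ratio is 1.

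**Rejection rates.** Simulated with normal data, equal means and nominal 5%, 200,000 runs per cell (Monte Carlo error about 0.1 point). The SD ratios are assumed. Each cell gives ratio 1.5 / ratio 2.

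| Split | Pooled, smaller arm more variable | Pooled, larger arm more variable |
|---|---|---|
| 18:18 | 5.1% / 5.3% | (arms equal) |
| 14:18 | 6.4% / 7.2% | 4.1% / 3.7% |
| 14:22 | 7.4% / 9.0% | 3.4% / 2.8% |
| 12:24 | 8.5% / 11.2% | 2.7% / 1.9% |

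Welch's test lies between 4.9% and 5.1% in every cell.

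**How likely such splits are.** Assume unrestricted allocation of 36, so that the cocoa arm size is Binomial(36, 0.5). An 18:18 split then has probability 13%. A cocoa arm of 14 or fewer has probability 0.243/2 = 12%, and of 12 or fewer 0.0652/2 = 3.3%. Placebo has the same chances. Averaged over all splits, with one arm more variable, the pooled test's error is 5.1%, 5.2% and 5.6% at SD ratios 1.25, 1.5 and 2.

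**A mechanism that would make spreads differ.** Suppose a fraction p of cocoa patients improves by D, the rest do not change, pD = 0.776, and response is unrelated to baseline score. The cocoa SD is then √(0.84² + p(1−p)D²).

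- p = 0.3: D = 2.59, SD = √(0.7056 + 1.405) = 1.453, ratio to 0.84 = 1.73.
- p = 0.5: D = 1.55, SD = √(0.7056 + 0.602) = 1.144, ratio 1.36.

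The means now differ, so the relevant quantity is coverage of a nominal 95% interval for the mean effect:

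| Cocoa:placebo | p | Pooled | Welch |
|---|---|---|---|
| 14:22 | 0.3 | 91.6% | 94.6% |
| 14:22 | 0.5 | 93.2% | 95.0% |
| 12:24 | 0.3 | 89.8% | 94.5% |
| 12:24 | 0.5 | 92.2% | 94.8% |

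**Cost of Welch when SDs are equal** (power for 0.776 with SD 0.84): 18:18, 76.8% to 76.7%; 14:22, 74.7% to 74.0%; 12:24, 71.8% to 70.3%.

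**The case against.** The case for leaving the plan alone is that the harm is conditional and usually small, and most of it stands.

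- **Equal arms are planned.** At 18:18 the pooled test is close to nominal, and averaged over random splits it stays near 5%. The 7% to 11% cells need an uneven split and greater spread in the smaller arm. A reader might quote the two-tailed chance of 14:22 or worse (24%) as the chance of harm. For a small cocoa arm it is half that, and in the mirror split the test is conservative.
- **Unrestricted allocation is inferred from silence.** Section 8.7 neither describes nor rules out a balanced list.
- **Unequal spread is assumed.** Section 8.4 gives a single SD. A reader might conclude that the cocoa arm must be the more variable one, but if patients with higher baseline scores improve more, its spread could shrink.
- **The rejection rates are not false-positive rates for the mechanism offered.** If cocoa affects nobody, the variances are equal and Student's test is valid. If it helps some patients, the means differ, and what suffers is interval coverage. The plan specifies no intervals.
- **The adherence rule is weak evidence of a shrinking cocoa arm.** Its wording names cocoa only, so a reader might infer that only that arm loses patients. The trial is double-blind, and section 8.6 defines the cocoa variable to include placebo as its absent level. Loose wording is the likelier reading.

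What survives is that the trial will analyse one realised split, that nothing described in the plan guarantees balance after eliminations, and that the remedy costs very little.

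**Conclusion.** The point holds as a low-cost improvement. Section 8.8 relies on a test that needs equal sizes or equal spreads, and the plan as written secures neither. If the final arms are about 14:22 and the SDs differ by a factor of 1.5 to 2, the nominal 5% test runs at about 7% to 9% or about 3%, depending on which arm is more variable. If 30% to 50% of cocoa patients respond and cocoa is the smaller arm, a pooled 95% interval covers about 90% to 93% at 14:22 to 12:24, against 94% to 95% with Welch.

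These sizes rest on assumed SD ratios, an assumed responder pattern and unrestricted allocation. With equal arms or equal spreads there is almost nothing to correct. The documents do not support a claim that the trial's false-positive rate is materially inflated overall, nor that the error must favour cocoa.

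**What to change.** In section 8.8 and in the Summary, replace Student's independent-samples t-test with Welch's t-test (unequal variances) for all between-arm comparisons of means. Apply it from the outset, without a preliminary test of variances.

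The change is one phrase in two places and needs no new data. The price with equal variances is the power loss shown above: about 0.1 point at 18:18, 0.7 at 14:22 and 1.5 at 12:24. Welch does nothing about bias from eliminating patients after randomisation, which needs separate treatment.
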